## 3.7. Biomarkers

### 3.7.1. Intracellular Biomarkers

Plasma concentrations of free Neu5Ac in subjects with GNE myopathy did not differ significantly from controls (see [Section 3.5.3.2](#)) likely because the intracellular biosynthesis only accounts for a proportion of the plasma sialic acid. Therefore, the measurement of intracellular biomarkers may be a more sensitive measurement in subjects with GNE myopathy. CMP-sialic acid is the end-product of the sialic acid biosynthesis pathway. This nucleotide-activated form of sialic acid is the donor of sialic acid to nascent glycoconjugates in the Golgi apparatus (Figure 1) and therefore may serve as a marker of successful restoration of the intracellular synthesis of biologically active sialic acid. The cellular CMP-sialic acid level is approximately 4-fold greater than free sialic acid. An LC-MS/MS method is being developed and validated to measure intracellular CMP-sialic acid and Neu5Ac levels in human white blood cells (WBC) pellets.

### 3.7.2. Lectin Staining of Muscle Biopsies

Hyposialylation of muscle proteins is thought to play a major role in GNE myopathy, re-sialylation of muscle proteins would prove biological efficacy. Furthermore, hyposialylation has been correlated with decreased muscle performance in heterozygous GNE knockout mice. Lectin staining has been useful to demonstrate hyposialylation particularly of O-linked glycans in the muscle of the mouse model and subjects with GNE myopathy. Sialylation of muscle glycans recovered to normal levels in our GNE myopathy mouse model after ManNAc therapy. This method is the only reported reproducible, quantifiable assessment of muscle glycan hyposialylation in GNE myopathy to date. We feel that these convincing lectin-staining data justify acquiring muscle biopsies from GNE myopathy subjects in this study at baseline and after 3 months of therapy (see [Section 5.2.4.](#))

### 3.7.3. Plasma Sialylated Proteins

Proteins that become sialylated in the Golgi and secreted in the plasma may serve as markers of the protein sialylation, in particular those with mucin-like O-glycan structures. We have data that show the ratio of the plasma O-glycan structures Thomson-Friedenreich (T)-antigen versus Sialyl T-antigen (T/ST ratio) is abnormal in subjects with GNE myopathy. We have anecdotal evidence that the plasma T/ST ratios normalized in GNE myopathy subjects that received sialylation-increasing therapies (including IVIG, off-label ManNAc, sialic acid). Exploratory glycan analysis can also be performed in subjects' blood as a way of identifying hyposialylated proteins that may serve as biomarkers.

## 3.8. Safety of ManNAc

### 3.8.1. Nonclinical Safety Evaluation

#### 3.8.1.1. 90-Day Rat and Dog Oral Toxicology Studies

The safety of ManNAc has been demonstrated by nonclinical 90-day toxicology studies conducted to support the use of ManNAc in rats (IND 78,091\_vol08\_11.2.4.3A\_2012 06 27.pdf) and dogs (IND 78,091\_vol11\_11.2.4.6A\_2012 06 27.pdf). Adverse effects noted were mainly gastrointestinal and included loose feces, mild mucosal hyperplasia of the colon, mild increase in alanine transaminase (ALT) and minimal to mild hepatocellular hypertrophy. The doses and length of the trial proposed in this protocol are supported by these 90-day toxicology studies (see [Appendix L](#)).

**Table 2. Maximum Recommended Starting Dose Based on 90-Day Toxicology Studies**

Species	NOAEL (mg/kg)	Conversion factor	HED (mg/kg)	Safety factor	MRSD (mg/kg)	MRSD *70 kg (mg/day)
Rats	12,000	*0.16	1,920	10	192	13,440
Dogs	6,000	*0.54	3,240	10	324	22,680
To convert Animal Dose in mg/kg to Human Equivalent Dose (HED) in mg/kg, multiply animal dose by conversion factor based on Body Surface Area. Maximum Recommended Safe Dose (MRSD) in mg/kg = HED/safety factor						

Given the findings in the toxicology studies, effects that may be seen in humans include loose stools, anemia, decreased albumin, increased BUN, increased transaminases and abnormal urinalysis, all of which are monitored as part of this protocol (See 5.2.2). Given our prior experience on the Single Ascending Dose trial (See 3.7.2.1) loose stools may be expected.

### 3.8.1.2. 26-Week Rat and 39-Week Dog Oral Toxicology Studies

The safety of ManNAc has been demonstrated by nonclinical toxicology studies of 26-weeks in rats and 39-weeks in dogs (Summarized in Appendix L; Tables 6 and 7):

- HLS study number BEQ0001 “Toxicity Study by Oral Gavage Administration to Beagle Dogs for 39 Weeks Followed by a 4 Week Recovery Period”, Huntingdon Life Sciences (final report issued October 17, 2014): The administration of ManNAc (ManNAc) was well tolerated and did not result in any evidence of treatment-related adverse toxicity in Beagle dogs after 39 weeks of oral gavage administration with N-Acetyl-D-mannosamine monohydrate (ManNAc) at doses of up to 4,500 mg/kg/day (1,500 mg/kg/dose three times daily), or after the 4 week recovery period.
- HLS study number BEQ0005 “Toxicity Study by Oral Gavage Administration to Sprague Dawley Rats for 26 Weeks Followed by a 4 Week Recovery Period”, Huntingdon Life Sciences (final report issued December 9, 2014)

**Table 3. Maximum Recommended Starting Dose Based on Long-Term Toxicology Studies**

Species	NOAEL (mg/kg/d)	Conversion factor	HED (mg/kg/d)	Safety factor	MRSD (mg/kg)	MRSD *70 kg (mg/day)	Target Organs
Rats	12,000	*0.16	1,920	10	192	13,400	GI, liver, adrenal, kidney
Dogs	4,500	*0.54	2,430	10	243	17,000	GI, liver, kidney
* Equivalent surface area conversion factor Maximum Recommended Safe Dose (MRSD) in mg/kg = HED/safety factor							

Given the findings in the toxicology studies, effects that may be seen in humans include loose stools, anemia, decreased albumin, increased BUN, increased transaminases and abnormal urinalysis, all of which are monitored as part of this protocol (See 5.2.2). Given our prior experience on the Single Ascending Dose trial (See 3.7.2.1) loose stools may be expected.

## 3.8.2. Clinical Safety

### 3.8.2.1. 12-HG-0207 (ClinicalTrials.gov Identifier: NCT01634750)

On the single-ascending dose (SAD) study, ManNAc was safe and well tolerated. All adverse events (AEs) observed in the study were Common Terminology Criteria for Adverse Events (CTCAE) Grade 1 or 2. There were no serious adverse events (SAEs). The frequency of AEs in Cohorts 1 and 2 (75% and 33%, respectively) was not higher than the frequency of AEs in subjects who received placebo (83%). Half of the subjects at the received 10,000 mg dose, had a single, self-resolving episode of loose stools (Grade 1) shortly after ingestion of ManNAc, which was not associated with abdominal pain or other gastrointestinal symptoms. Diarrhea was not reported at lower doses (Cohorts 1 and 2) or in the placebo group and was likely caused by unabsorbed ManNAc in the gastrointestinal tract, suggesting that absorption of ManNAc is saturated when giving 10,000 mg as a single dose. Therefore a single dose of 10 grams was considered the Maximum Tolerated Dose. See [Appendix F](#) for a list of study AEs.

#### **3.8.2.2. 15-HG-0068 Open-Label Phase 2 Study (ClinicalTrials.gov Identifier: NCT02346461)**

There have only been no Serious Adverse Events observed as part of this Open-Label Phase 2 Study. The SRC review included safety through 24 months on all subjects. The reviewed safety information included adverse events (AEs), ECGs, vital signs, physical assessments and clinical laboratory data. Eight subjects remain on 6 grams twice daily. Four subjects have withdrawn consent, two of which discontinued due to gastrointestinal tolerability, another planning on getting pregnant and another was withdrawn due to noncompliance. AEs for the cohort from the latest SRC review are in [Appendix G](#). Due to 8 out of 12 subjects participating in this trial, demonstrated gastrointestinal tolerability issues or AEs related to ManNAc and 16% had tolerability issues significant enough to discontinue their participation, we have attempted to better understand the etiology of the decreased tolerability. The clinical manifestations together with PK evaluations, strongly suggest that unabsorbed ManNAc in the gastrointestinal tract is the likely cause. As discussed below in [Section 3.9.1](#), we believe absorption of ManNAc can be increased by 20% by giving the same daily dose of ManNAc (12 grams) divided three times (4 grams TID) instead of twice daily (6 grams BID).

One subject in the study had Grade 3 hypertriglyceridemia which was determined to be probably related to ManNAc. As higher triglycerides were also seen in toxicology studies (see [Table 10](#)), hypertriglyceridemia is a risk associated with ManNAc.

#### **3.8.3. Preliminary Findings 15-HG-0068 Open-Label Phase 2 Study**

##### **3.8.4. Pharmacokinetic Model for ManNAc and Sialic Acid in GNE Myopathy Subjects**

Serial-sampled plasma ManNAc and Neu5Ac concentrations obtained from the SAD study (see [Section 3.5.3](#)) and from this Open-Label Phase 2 study were used to develop a semi-mechanistic population model to simultaneously characterize ManNAc and Neu5Ac plasma concentrations following single or repeated oral doses of ManNAc to GNE myopathy subjects. The model showed that oral bioavailability of ManNAc decreased with increase in oral dose, likely due to decreased absorption. Simulations using this PK model also demonstrated that administering the same daily dose divided in three doses (4,000 mg every 8 hours) rather than twice daily can improve tolerability, increase bioavailability by ~20%, and boost ManNAc and Neu5Ac exposures (See [Table 4](#)). Based on this, we will evaluate the PK of 4 grams TID dosing during the 30-month visit.

**Table 4. Simulations of ManNAc Dose and Frequency using the Semi-Mechanistic Population PK Model for GNE Myopathy.**

ManNAc dose and frequency	ManNAc CSS ave Mean (ng/mL)		Neu5Ac CSS ave Mean (ng/mL)	
	on Day 1	On Day 30	on Day 1	on Day 30
4,000 mg TID	923	1150	189	965
6,000 mg BID	878	952	219	826
12,000 mg QD	693	698	254	645

\*Based on simulation run N=90 in a structural PK/PD model.

Abbreviations: CSS, steady state concentration; TID, three times daily; BID, twice daily; QD, once daily.

### 3.8.5. Muscle Strength

One of the secondary objectives of the Phase 2 study is to evaluate suitable endpoints for future trials. Because there is muscle atrophy and replacement of muscle by fibro-fatty tissue as part of the disease process, reversal of disease progression is unlikely. Rather, a slowing in the rate of progression is the expected treatment effect.

As part of this, muscle strength measured by QMA has been collected at every visit. All 12 patients participating in the open-label study were prior participants of the Natural History Study, and therefore, their ‘natural history’ rate of progression (prior to ManNAc administration) has been determined.

To evaluate the performance of the disease progression model when incorporating treatment effect, data from the Phase 2 was tested in the model, to compare the rate of progression after initiation of ManNAc to the rate of progression before intervention. At 182 days (6 months), a preliminary analysis shows a posterior mean of  $\gamma=0.49$  (95% CI: .02-1.35). At 182 days (12 months), another preliminary analysis shows the current mean estimate for  $\gamma$  is approximately 0.61 (95% CI (0.09, 1.27), and the posterior probability that  $\gamma$  is less than 1 is 0.89. The most recent analysis at 548 days (18 months), shows a  $\gamma=0.55$  with a posterior probability that  $\gamma$  is less than 1 is 0.966. This means, the model estimates a 45% slowing in the rate of decline on subjects receiving ManNAc with a probability that there has been slowing in progression of 96.6%.

## 4. STUDY DESIGN

### 4.1. Study Overview

This is a Phase 2, open-label, single-center study of ManNAc in subjects with GNE myopathy. The study will characterize the safety, tolerability and PK of multiple doses of ManNAc (Pharmacokinetic Phase), intermediate (90-day), and long-term (912 days; 30 months) safety and efficacy of ManNAc (Safety and Efficacy Phase). Twelve subjects will be enrolled into the trial.

Before dosing, subjects will undergo baseline evaluations that include clinical laboratory tests, muscle biopsy, Quantitative Muscle Assessment (QMA), muscle MRI, muscle biopsy and patient-reported outcomes (PROs).

In the pharmacokinetic (PK) phase, subjects will receive one of two doses: 3,000 mg (Cohort A) or 6,000 mg (Cohort B) ManNAc twice daily (BID) for total daily doses of 6,000 and 12,000 mg, respectively for 7 days while admitted to the NIH Clinical Center to assess for PK and safety. Safety and tolerability will be assessed on an individual basis.

In the Safety and Efficacy Phase, if ManNAc was safe and well-tolerated in the PK phase, subjects on Cohort A will be escalated to 6,000 mg BID on Day 7, and safety of the new dose-level will be assessed until discharge on Day 10. Subjects on Cohort B will be maintained at 6,000 mg BID, and if well tolerated they may be discharged on Day 7. After discharge, subjects will self-administer ManNAc at a dose of 6,000 BID for a total dosing duration of 912 days (30 months).

Follow-up visits to the NIH Clinical Center will occur on Day 45 ( $\pm 7$ ), Day 85 ( $\pm 7$ ), Day 180 ( $\pm 14$ ), Day 365 ( $\pm 14$ ), Day 548 ( $-30$ ), Day 730 ( $-30$  days) and Day 912 ( $-30$  days). PK, PD and safety will be evaluated at all visits. Muscle biopsy will be performed only at the baseline and Day 85 visits.

Follow-up phone calls for safety will occur at approximately Days 28, 63, 120, 240, 300, 400, 638, and 820 ( $\pm 30$  days). After Day 912 all Grade  $\geq 2$  AEs at least possibly related to study drug will be followed to resolution.

### 4.2. Sample Size

A sample size of 12 GNE myopathy subjects was selected for this study to provide information on the safety, PK and biochemical efficacy of ManNAc.

### 4.3. Visit Schedule

**Table 5. Brief Visit Schedule**

Window	Description	Relative Day	
		Min	Max
Day -30 to -1	Screening Phase	-30	-1
Day -7 to 0	Baseline Phase	-7	0
Day 1-90	Treatment Phase		
Day 1-7	PK Phase (inpatient)	1	7
Day 7-90	Safety/Efficacy Phase	7	90
Day 45 ( $\pm 7$ days)	Follow-up Evaluation	38	52

Day 85 ( $\pm$ 5 days)	3 month Follow-up evaluation	80	90
Day 180 ( $\pm$ 14 days)	6 month Follow-up evaluation	166	194
Day 365 ( $\pm$ 14 days)	12 month Follow-up evaluation	351	365
Day 450 ( $\pm$ 30 days)	Optional for blood draw		
Day 548 (- 30 days)	18 month Follow-up evaluation	534	562
Day 638 ( $\pm$ 30 days)	Safety labs and phone or email follow-up	608	668
Day 730 (- 30 days)	24 month Follow-up evaluation at NIH CC	700	730
Day 820 ( $\pm$ 30 days)	Safety labs and phone or email follow-up	790	850
Day 912 (- 30 days)	30 month Follow-up evaluation at NIH CC	882	912

See [Appendix C](#) for the Schedule of Events and [Appendix D](#) for blood and urine sampling schedule.

## 4.4. Dose and Frequency

### 4.4.1. Dose Levels

The ManNAc doses to be investigated (3,000 and 6,000 mg BID for a total daily dose of 6,000 and 12,000 mg, respectively) are based on the safety and PK data collected in NIH Study 12-HG-0207 (See [Section 3.5.3](#)). In that study, a single dose of 10,000 mg ManNAc was associated with diarrhea and there was no difference in the  $C_{max}$  or AUC of plasma Neu5Ac between the doses of 6,000 or 10,000 mg, suggesting saturation in the enzymatic rate of the Neu5Ac biosynthesis pathway or the transport of ManNAc into the cell. Therefore, the maximum single dose of ManNAc to be used in this study will be 6,000 mg per dose, for a total of 12,000 mg per day.

The administration of maximum dose of 12,000 mg ManNAc per day for 90 days is covered by the 90-day toxicology studies performed in rats and dogs. As mentioned in [Section 3.8](#) and shown in [Appendix L](#), effects on the gastrointestinal tract were the most prominent toxicology findings, and included loose and discolored feces, mild liver enlargement, and mucosal hypertrophy of the colon. Given these findings, the NOAEL was determined to be 12,000 mg/kg/day in rats and 6,000 mg/kg/day in dogs. It was determined that the human equivalent dose (HED) is 1,714 mg/kg/day, or approximately 12,000 mg/day based on the NOAEL observed in rats, the most sensitive species, with a 10-fold safety factor.

Administration of a maximum dose of 12,000 mg ManNAc for up to one year is covered by the long-term toxicology studies performed in rats (26 weeks) and dogs (39 weeks), as shown in [Appendix M](#).

[figure not shown]
If any safety issues occur during the pharmacokinetic phase (Day 1-10) either detected clinically or based on laboratory values, those subjects will be continued on a lower dose for the safety and efficacy phase of the trial.

### 4.4.2. Dose Frequency

A ManNAc dose frequency of every 3,000 or 6,000 mg every 12 hours (BID) was selected based on the sustained elevation of plasma free Neu5Ac with a  $T_{max}$  of 8-11 hours ([Table 1](#)), and levels returning to baseline by 24 hours after a single dose of 3,000 mg of ManNAc but remaining above baseline values by 48 hours after single dose of 6,000 or 10,000 mg of ManNAc ([Figure 4](#)) and supported by simulated plasma concentration-time profiles of ManNAc and free Neu5Ac after 6,000 mg of ManNAc BID (12,000 mg per day) were generated to estimate the time to reach steady-state after multiple doses ([Figure 5](#)). No

significant accumulation of ManNAc is predicted following BID dosing of 6,000 mg of ManNAc due to the short half-life of ManNAc (2-3 hours), and supported by the rat and dog toxicokinetic reports; however, an accumulation for free Neu5Ac is desired and expected due to its longer half-life (Figure 5), although it does not increase above a certain threshold, as evidenced in the toxicokinetic reports in rats (IND 78,091\_vol08\_11.2.4.3A\_2012 06 27.pdf) and dogs (IND 78,091\_vol11\_11.2.4.6A\_2012 06 27.pdf), likely due to the feedback inhibition in the sialic acid biosynthetic pathway (Figure 1).

**Figure 5. Simulated Concentration-Time Profiles for Plasma (A) ManNAc and (B) Free Neu5Ac with ManNAc 6,000 mg BID in Subjects with GNE Myopathy**

## 4.5. Dose Administration

### 4.5.1. Inpatient Drug Administration

Inpatient drug administration will be performed with the purpose of determining PK parameters. The study drug will be prepared in individual doses of powder in bottle (PIB) by the NIH Pharmacy and sent to the inpatient unit. The study drug will be administered orally by the CC nursing staff BID on Days 1-7, or TID starting on Day 912-914 (+/- 30 days). Subjects will take study drug on an empty stomach, at least 2 hours before a meal and 1 hour after a meal. Water may be taken at all times.

For the morning dose on Days 1 and 7, and Days 912-914, the dose will be given after an overnight fast. Breakfast on Days 1 and 7 may be eaten 1 hour after the morning dose is given. The sample schedule below will be followed, whenever possible; when there is a modification in dosing or other unforeseen delay, the schedule will be adjusted accordingly:

Day 1		Day 2-6 (days with PK trough only)	
Midnight-0900:	Water only	0500-0600	Breakfast. No food after 0700
0800:	Morning DOSE	0600-0900	Water only
0800-0900:	Water only	0800:	Morning DOSE
0900-1800:	Regular diet (no restrictions)	0800-0900:	Water only
1800-2000:	Water only	0900-1800:	Regular diet (no restrictions)
2000:	Evening DOSE	1800-2100:	Water only
2000-2100:	Water only	2000:	Evening DOSE
2100:		2000-2100:	Water only

	Bedtime snack (if desired)	2100:	Bedtime snack (if desired)
Day 7		5-7 days before Day 912	
Midnight-0900: 0800: 0800-0900: 0900:	Water only Last DOSE Water only May resume regular diet		No ManNAc intake
Days 912-914			
Midnight-0800: 0800: 0800-0900: 0900-1400: 1400-1600: 1600: 1600-1700:	Water only Morning DOSE Water only Regular diet Water only Afternoon DOSE Water only	1700-2200: 2200-2400: 2400: 2400-:	Regular diet (no restrictions) Water only Evening DOSE Water only

#### 4.5.2. Drug Administration after Discharge

After completion of PK studies on Day 1-7, subjects will be discharged and study drug will be self-administered while not admitted to the NIH CC. The study drug will be provided as a canister of bulk powder that will be measured with a Spatula Balance™. During the inpatient stay, subjects will be taught proper dosing and administration techniques. Subjects will take the study drug BID within 15 minutes of breakfast and dinner.

Subjects returning to their 30-month visit will be asked to stop the intake of ManNAc for 5-7 days before admission to perform PK testing of TID dosing.

#### 4.5.3. Drug Administration During Terminal Half-Life PK Determination

Terminal half-life will be determined during the Day 85 visit. While the subject is inpatient, the study drug will be withheld for 72 hours with the purpose of determining terminal half-life PK parameters.

Day 85			
Midnight-0 0: 0800: 0800-0900: 0900:	Water only Terminal half-life DOSE Water only May resume regular diet		

#### 4.6. Concomitant Medications

Subjects must be willing to stop treatment with ManNAc, sialic acid, IVIG, and/or other supplements containing sialic acid (e.g., St John's wort, sialyllactose) 90 days before initial dosing and remain off these medications for the duration of the trial. Prescription medications and supplements will be

maintained at a constant level throughout the duration of the study, unless dose adjustment is clinically necessary. Such adjustments will be recorded in the patient's CRF.

#### **4.7. Safety Evaluations**

Safety will be assessed by adverse events (AEs), vital signs, physical examinations, and clinical laboratory tests (See 5.2.2) and classified based on the Common Terminology Criteria for Adverse Events (CTCAE), Version 4.03.

#### **4.8. Dose Escalation**

Subjects in Cohort A will receive 3,000 mg of ManNAc BID for 7 days before they are escalated on Day 7 to receive 6,000 mg BID for the rest of the trial. The evaluation of a dose escalation/de-escalation for an individual will initially be reviewed by the Principal Investigator, according to the criteria in Table 5 and reviewed by the Safety Review Committee (SRC) when the Cohort is completed or safety issues arise. The safety information to be reviewed will include AEs, physical exams, vital signs, and clinical laboratory data.

##### **4.8.1. Escalation and Continuation Rules for Cohort A**

Subjects in Cohort A will receive 3,000 mg of ManNAc BID for 7 days before they are escalated to receive 6,000 mg BID for the rest of the trial:

[figure not shown]
- a. Subjects in Cohort A will be escalated to 6,000 mg BID on Day 7 if no serious AEs and no more than 2 Grade 2 drug-related AEs occur.
- b. If subjects experience  $\geq 2$  Grade 2 drug-related AEs or  $\geq 1$  drug-related SAE at 3,000 mg BID, the SRC will be convened to make escalation/de-escalation decisions based on Table 5.
- c. The subjects will continue on 6,000 mg BID until they experience  $\geq 2$  Grade 2 drug-related AEs or  $\geq 1$  drug-related SAE. In this case, the SRC will be convened to make decisions based on Table 5.

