##### **4.8.2. Initiation and Continuation Rules for Cohort B**

The SRC will review all available safety data for Cohort A of subjects prior to making a decision to initiate Cohort B. The SRC will convene when at least 14 days of safety have been collected on the last subject dosed in Cohort A.

- a. Cohort B will be initiated at 6,000 mg BID provided that there are  $< 2$  subjects in Cohort A that experienced  $\geq 2$  Grade 2 drug-related AEs or  $\geq 1$  drug-related SAE.
- b. If subjects experience  $\geq 2$  Grade 2 drug-related AEs or  $\geq 1$  drug-related SAE, the SRC will be convened to make decisions based on Table 6.

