**Figure 6. Dosing Escalation/De-escalation**

Table 6. Dose Escalation/De-escalation Rules	
Safety Profile*	Safety Review Committee Decisions*
No SAEs and Any number of CTCAE Grade 1 drug-related AEs or ≤ 1 CTCAE Grade 2 drug-related AE	Continue per protocol
2 CTCAE Grade 2 drug-related AEs	Continue per protocol, or study a lower dose § ,
≥ 3 CTCAE Grade 3 drug-related AEs	Study a lower dose § , or Withdraw the subject, and Convene SRC to evaluate the risk/benefit profile for dose escalation of other subjects
Any CTCAE Grade 4 AE; or ≥ 1 drug-related SAE Determination that the limit of safety and/or tolerability has been reached	Withdraw the subject, and Evaluate the risk/benefit profile in other subjects for dose escalations to or above the dose resulting in Grade 3 toxicity, and Discontinue study if 2 subjects develop the same Grade 3 toxicity or if any subject develops a Grade 4 toxicity

The safety decisions in this table apply only to safety and tolerability in an individual subject. If a decision is made that the dose escalation stopping criteria have been met, this does not preclude the use of the remaining subjects to evaluate the safety, PK, and PD effects of lower doses of ManNAc with the assessments described in this protocol.
 
*Note: Subjects from both Cohort A and Cohort B on 6,000 mg BID count toward the number of subjects experiencing toxicity.
 
§ Lower doses to study may include 4,500 mg BID, 3,000 mg BID or 2,000 mg BID depending on dose level where toxicity occurred.
	

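### At exactly two Grade 2 drug-related AEs, Section 4.8.1 both escalates a Cohort A subject and refers that subject to the SRC; separately, one or two non-serious Grade 3 drug-related AEs have no count trigger for SRC review

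*Combined protocol and SAP*

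**What the plan says.** Section 4.8.1 governs Cohort A, which starts on 3,000 mg BID. Rule (a) says subjects will be "escalated to 6,000 mg BID on Day 7 if no serious AEs and no more than 2 Grade 2 drug-related AEs occur". Rule (b) starts at two or more Grade 2 drug-related AEs, or one drug-related SAE, on 3,000 mg BID; then "the SRC will be convened to make escalation/de-escalation decisions based on Table 5". Rule (c) covers dosing after escalation: "The subjects will continue on 6,000 mg BID until they experience" the same two-or-more Grade 2 count or a drug-related SAE. Section 4.8.2(b) uses that count for Cohort B, and there "the SRC will be convened to make decisions based on Table 6".

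Table 6 holds the rules. Row 1 covers "No SAEs and Any number of CTCAE Grade 1 drug-related AEs", or at most one Grade 2 drug-related AE, and continues. Row 2 covers two Grade 2 drug-related AEs, and the SRC may "Continue per protocol, or study a lower dose". Row 3 is at or above "3 CTCAE Grade 3 drug-related AEs". The last row covers any Grade 4 AE, any drug-related SAE, and a judgement entry: "Determination that the limit of safety and/or tolerability has been reached". Its action column also stops the study if two subjects have the same Grade 3 toxicity. Section 4.9 convenes the SRC to consider dose modification at more than two Grade 2 drug-related AEs, or at Grade 1 or 2 events that limit tolerability.

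**The concern.** An escalation rule should give one answer for each safety profile. At exactly two Grade 2 events, Section 4.8.1 gives two. Under (a) the subject moves from 6,000 to 12,000 mg per day. Under (b) a committee decides, and it may hold or lower the dose.

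The second problem is one of ordering. Two Grade 2 events bring a subject to the SRC by count, but two non-serious Grade 3 events do not, although they are more severe. The case is not hypothetical. Section 3.8.2.2 reports Grade 3 hypertriglyceridemia judged probably related to ManNAc. That section and 9.1.1 report no SAEs, so the event was non-serious. Because Table 6 ends the study when a second subject has the same Grade 3 toxicity, the first such event should have a defined route to the SRC.

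**Working it through.** The plan gives no figure to reproduce; the check sets the rules side by side. Counts are taken per subject, because the note under Table 6 applies its decisions to the individual.

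**Step 1: Grade 2 counts, with no SAE and no Grade 3 or 4 event.**

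| Grade 2 drug-related AEs | 4.8.1(a) escalate | 4.8.1(b) SRC | 4.9 count | Table 6 |
|---|---|---|---|---|
| 0 | met | not met | not met | row 1 |
| 1 | met | not met | not met | row 1 |
| 2 | met | met | not met | row 2 |
| 3 or more | not met | met | met | no row |

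Rule (a) accepts {0, 1, 2} and rule (b) accepts {2, 3, ...}. They overlap at 2 and nowhere else. Three or more Grade 2 events also lack a Table 6 row, but 4.9 supplies the action, so that is not a gap in the rules.

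**Step 2: which rule is out of line.** Table 6 row 1 ends at one Grade 2 event and row 2 gives the SRC a choice at two. Rule (c) and Section 4.8.2 also draw the line at two. Moving (a) to at most one gives {0, 1} against {2, 3, ...}: no overlap, and agreement with rows 1 and 2. Moving (b) to three or more would also remove the overlap, but row 2 would then have no matching trigger in 4.8.1.

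**Step 3: Grade 3 events.** Take one or two non-serious Grade 3 drug-related AEs, at most one Grade 2 event, no SAE and no Grade 4 event.

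- 4.8.1(a) does not mention Grade 3, so its wording does not stop escalation.
- 4.8.1(b), 4.8.1(c) and 4.8.2(b) count only Grade 2 events and SAEs. None is met.
- 4.9 names only Grade 1 and Grade 2 events. Its count is not met.
- Table 6 rows 1 and 2 name Grades 1 and 2. Row 3 starts at three Grade 3 events. The last row needs a Grade 4 event, a drug-related SAE or the judgement entry. No row names this profile.

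**Step 4: cross-references.** Sections 4.8 and 4.8.1 point to Table 5, which is the visit schedule in 4.3. Section 4.8.2(b) points correctly to Table 6.

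**The case against.** The strongest reply is that other text surrounds these rules. Section 4.1 makes Cohort A escalation conditional on the drug having been safe and well tolerated in the PK phase. Section 4.8 has the investigator review each subject first. Section 4.4.1 moves subjects with safety issues in the first ten days to a lower dose. A reader might infer from (a) alone that the dose doubles automatically; these provisions mean that it does not. They do not settle the conflict, though. None ranks (a) against (b), and 4.4.1 does not define a safety issue. The outcome may also be the same either way, since continuing is one of the SRC's options in row 2.

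The more-than-two threshold in 4.9 agrees with (a), so (a) does not stand wholly alone. But 4.9 concerns dose modification and does not say that it overrides (b).

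On Grade 3, the sequence at most one, two, at least three suggests that row 3 may be a misprint of the grade. Figure 6 is not shown in the text reviewed and could name a Grade 3 action. Both points stand, and they limit confidence in this part. Figure 6 could not remove the conflict between the words of (a) and (b).

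Oversight is also wider than the count rules. Section 4.8 provides SRC review when safety issues come up, 12.1.2 and 12.3.1 provide ongoing and regular SRC review, and 12.3.2 provides yearly DSMB review of all AEs. Table 6 has its judgement entry. What is missing is a defined trigger and a stated action.

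Finally, little escalation remains. Accrual was planned for January to June 2015 and safety through 24 months has been reviewed. The (a)/(b) conflict can arise now only if a replacement subject enters Cohort A. Sections 5.9 and 6.1 provide for replacement, but none is reported.

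**Conclusion.** The contradiction in 4.8.1 is certain on the text. It is confined to one count, exactly two Grade 2 drug-related AEs with no SAE, and its practical reach is now limited to replacement subjects.

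The Grade 3 gap holds on the visible text, subject to row 3 and Figure 6 being as they appear. It applies to continued dosing: Section 3.8.2.2 reports eight subjects still on 6 g twice daily, and 1 of the 12 enrolled has had a non-serious Grade 3 related event.

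Two stronger readings are not supported. A reader might infer that row 1 tells the SRC to continue a subject with a Grade 3 event; row 1 names only Grades 1 and 2, so the fair statement is that Table 6 is silent. A reader might also infer that the observed Grade 3 case escaped review; its timing and the dose at onset are not given, the SRC reviewed AEs and laboratory data through 24 months, and nothing shows that it was mishandled.

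Both parts should be corrected because they are safety rules and the correction costs almost nothing.

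**What to change.** 1. Reword 4.8.1(a) so that escalation requires no serious AE, no drug-related AE of Grade 3 or higher, and at most one Grade 2 drug-related AE.
2. Check Table 6 row 3 and Figure 6 against the intended rule. Then add one or more Grade 3 drug-related AEs to the SRC triggers in 4.8.1(b), 4.8.1(c) and 4.8.2(b), with a Table 6 row that lets the SRC continue, lower the dose or withdraw the subject.
3. Change the Table 5 references in 4.8 and 4.8.1 to Table 6.

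The cost is protocol wording and one table row in the next amendment, plus slightly more frequent SRC review. No dose reduction or withdrawal becomes mandatory, and no visit or procedure is added.
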